Those assigned to the docu-drama may be at risk of contracting COVID-19 if safety protocols are not adhered to during group meetings. To mitigate this risk, the viewing of the docu-drama will be held in a spacious environment where social distancing can be observed and participants will be seated six feet apart. All participants to be required to wear study provided face masks, adhere to socially distanced seating markers and walking directions, and other COVID-19 safety protocols.

There is also the potential of participants assigned to the WhatsApp group posting comments or images that may be upsetting to others. Participants will be given guidelines to follow to mitigate these risks. Participants will have access to each other's personal information (names and phone numbers). They may also share other personal details or experiences, all of which should be kept strictly confidential. This may lead to a breach of confidentiality for participants. From the outset, participants will sign a confidentiality agreement, in which privacy and confidentiality (and how they can be breached) will be explained, and participants will agree to uphold confidentiality and privacy throughout.

Known Potential Benefits

This study is expected to lead to increased motivation to repeat blood donation. Learning about the challenges around blood donation will help us to address these in the future. This could have a very important impact on patients who require blood transfusion as part of their medical treatment and will hopefully save many lives.

Safety Assessment

Definitions

Adverse Event (AE)

This is a socio-behavioural study, and thus clinical adverse events are unlikely.

Potential risks may include breach of confidentiality, and any discomfort that may result from WhatsApp group participation, discussions of the docu-drama group meetings, or issues about blood donation. In other words, while we will make every effort to de-identify any information participants share with the team, it may not be possible to keep their identity completely anonymous from those who may know their role closely. However, these risks are minimal and are not more than those encountered in everyday life.

There is also the potential of participants assigned to the WhatsApp group posting comments or images that may be upsetting to others. Participants will be given guidelines to follow to mitigate these risks, and a moderator will monitor the group interactions.

Serious Adverse Event (SAE)

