
Serious adverse events (SAEs) are defined as the following:

- Death
- Life-threatening (i.e., an immediate threat to life)
- Hospitalization or prolongation of hospitalization
- Persistent or significant incapacity or substantial disruption of the ability to conduct normal life functions
- Congenital abnormalities/birth defects

Other important medical events that may jeopardize the participant and/or may require intervention to prevent one of the outcomes listed above.

This study does not anticipate any serious adverse events.

Data Analysis

Qualitative Data Analysis

All qualitative data collection will proceed simultaneously with data analysis.

Focus group discussions and key informant interviews will be audio recorded with consent from the participants. The recorded interviews and focus group discussions will be tracked and uploaded to the DCC secure server. The recorded information will be transcribed verbatim and will be translated where appropriate.

The framework method will be used for data analysis. This is in part because of the multi-disciplinary team involved in the research (Gale et al., 2013) and use of a-priori themes (Srivastava & Thomson, 2009). The framework analysis will have five steps (Srivastava & Thomson, 2009).

1. Familiarization: Researchers will read the transcripts thoroughly to gain an understanding of the qualitative data collected.

2. Identifying a thematic framework: Researchers will identify key themes from the transcripts. The themes will be determined a-priori, but other themes that emerge will be identified. The themes will include barriers to becoming a repeat donor and motivations for being a repeat donor. These themes will be used to guide intervention development, and to assess secondary outcomes.

3. Indexing: Researchers will identify portions or sections of the data that match particular themes.

. Charting: This will involve arranging specific pieces of data that were indexed in the previous stage into charts. This means that the data will be lifted and placed in charts that consist of the headings and subheadings that were drawn during the thematic framework, or from a priori research inquiries or in the manner that is perceived to be the best way to report the research.

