The DSMB will review the quality and completeness of study data and enrollment data at each meeting to ensure proper trial conduct. Study personnel should provide any new literature particularly pertinent to the trial, along with their recommendation as to whether it affects the trial conduct or design. The DSMB will review the consent periodically and/or as needed and consider whether the consent form requires revision in light of any new findings or amendments.

Expected Outcomes of the Study

This study will contribute to the literature the use of communication interventions for promoting repeat blood donation in Ghana. The findings could influence the design of socio-behavioral interventions to positively influence blood donation in Ghana. Increased blood donation will lead to improved health outcomes.

Dissemination of Results and Publication Policy

At the end of the study, we will disseminate the results through

- Report to the Ghana Health Service
- Report to the National Blood Service, Ghana
- Report to our funder
- Publications in peer-reviewed journals
- Conference presentations
- Mass media

Problems Anticipated and Unanticipated

We anticipate that some respondents may not be willing to take part in the study.

Unanticipated Problems

An Unanticipated Problem (UP) is any incident, experience, or outcome that is:

1. Unexpected in terms of nature, severity, or frequency in relation to:
 - a. **the research risks that are described in the IRB-approved research protocol and informed consent document; or other study documents; and**
 - b. the characteristics of the population being studied; and
2. Possibly, probably, or definitely related to participation in the research; and
3. **Places study participants or others at a greater risk of harm (including physical, psychological, economic, or social harm) than was previously known or recognized.**

Furthermore, an UP could be an expected event that occurs at a greater frequency than would be expected based on current knowledge of the disease and treatment under study. The DSMB providing oversight to the study may make such an assessment based on an aggregate analysis of events.

Participants who attend the viewing of the docu-drama will be seated six feet apart, with all participants being required to wear face masks (individual or study provided), observe social distancing, handwashing, use of study provided hand sanitizers, and adhere to any new COVID-19 safety protocols.

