Attach a PID label here:

Bloodsafe Logo
Placeholder

Provide information for yourself and people you know who will be able to tell us how you are doing if we are unable to contact you. This information is confidential and will not be disclosed to anyone outside the study.

A. Volunteer Information

1. Name: _____
2. Telephone numbers:
 - a. Primary _____
 - b. Alternate _____
3. Address: _____

B. Information for Contacts

1. First contact
 - a. Name: _____
 - b. Telephone number: _____
 - c. Address: _____
 - d. Relationship to volunteer: _____
2. Second contact
 - a. Name: _____
 - b. Telephone number: _____
 - c. Address: _____
 - d. Relationship to volunteer: _____

13. Protocol Deviation Form

Protocol Deviation

Attach a PID label here:

Date of Site Awareness:

(example: 01-APR-2021)

		2	0	2	
Day	Month	Year			

Sequence:

--

*

Participant Initials:

--	--	--

Site:

--	--

Bloodsafe Logo

Placeholder

- 01 Korle-Bu Bld Bank
- 02 Korle-Bu Maternity
- 03 Pentecost Hospital
- 04 LEKMA Hospital
- 05 Maamobi Polyclinic
- 06 Accra Shopping Mall
- 07 Mobile Unit

*Sequence number across all deviations for this patient

Indicate the type of protocol deviation. Complete a separate form for each deviation.

1. Type of deviation; related to:

1 Informed consent

2 Eligibility

3 Visit procedures

4 Other deviation, specify; _____

2. Provide a brief narrative of the deviation:

3. Is this deviation considered:

1 Minor deviation

2 Major deviation

4. Date of deviation:

(example: 01-APR-2020)

		2	0	2	
Day	Month	Year			

5. Date this form completed:

(example: 01-APR-2020)

		2	0	2	
Day	Month	Year			

PI/Designee: _____

Date: _____

14. Serious Events (SAEs) Report Form

SAE

Participant ID:

SAE Number
(for this participant):

Each SAE must be given a unique number within that participant's record.

Participant
3-letter code:

		
----------------------	----------------------	----------------------

Bloodsafe Logo
Placeholder

01 Korle-Bu Bld Bank
02 Korle-Bu Maternity
03 Pentecost Hospital
04 LEKMA Hospital
05 Maamobi Polyclinic
06 Accra Shopping Mall
07 Mobile Unit

Site:

Complete this form to report any serious events (SAEs) the participant experiences during C-CAD.

A. Primary Event

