Be as specific as possible. Record the diagnosis (disease or clinical syndrome), if known. If a diagnosis has not been made, record the sign or symptom that is the most important in your clinical judgement. In the case of death, record the event that resulted in death. DO NOT write "Death" as the primary event. If the cause of death is unknown, write "death of unknown cause" as the primary event.

1. Record **one** primary event: _____

2. Date signs and symptoms related to the event began: (example: 01-AUG-2021)

			 2	 0	 2	
Day	Month	Year				

3. Date event became serious: (example: 01-AUG-2021)

			 2	 0	 2	
Day	Month	Year				

4. Date site became aware that event was reportable (serious): (example: 01-AUG-2021)

			 2	 0	 2	
Day	Month	Year				

5. Indicate the reason(s) the event is considered serious (**mark all that apply**):

- 1 Death → **Complete the Death CRF**
- 2 Life-threatening event (i.e., an immediate threat to life)
- 3 Hospitalization or prolongation of hospitalization
- 4 Persistent or significant incapacity or substantial disruption of the ability to conduct normal life functions

6. Indicate the current status of the event:

- 1 Resolved → 7. Date of resolution: (example: 01-AUG-2021)

			 2	 0	 2	
Day	Month	Year				
- 2 Resolved with sequelae
- 3 Not resolved
- 4 Chronic, not expected to resolve
- 5 Resulted in death → **Complete the Death CRF**
- 6 Participant died with event unresolved → **Complete the Death CRF**
- 7 Unknown

SAE

Bloodsafe Logo
Placeholder

Participant ID:**SAE Number
(for this participant):** **Participant
3-letter code:**

		
----------------------	----------------------	----------------------

B. Event Summary

Explain the chain of events and provide appropriate details to describe the event and put it in the context of the participant's experience in the study. The summary should include:

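### The SAE form does not match the protocol's own SAE definition, and no form systematically asks about the non-serious harms the protocol names

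*Combined protocol and SAP*

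**What the plan says.** **Seriousness.** Under Safety Assessment, the protocol opens its list with "Serious adverse events (SAEs) are defined as the following". Five bullets follow: death, threat to life, hospitalization, incapacity and birth defects. A closing sentence adds a sixth category: "Other important medical events that may jeopardize the participant and/or may require intervention to prevent one of the outcomes listed above". The section then says that no SAEs are anticipated.

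**The form.** The SAE Report Form (Study Tool 14) is limited to serious events: "Complete this form to report any serious events (SAEs) the participant experiences during C-CAD". Section A, item 5 asks the site to "Indicate the reason(s) the event is considered serious" and gives four boxes. Section B is a free-text narrative.

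**Unanticipated problems.** The section of that name requires an event to be unexpected, to be "Possibly, probably, or definitely related to participation in the research", and to raise risk above what was known. It adds that an expected event can qualify if it is too frequent, and that the DSMB "may make such an assessment based on an aggregate analysis of events".

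**Expected harms.** Under Adverse Event, the protocol says: "Potential risks may include breach of confidentiality, and any discomfort that may result from WhatsApp group participation". It also names upsetting posts or images, and under Risk/Benefit Assessment it notes that WhatsApp participants will see each other's names and phone numbers.

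**The concern.** The protocol expects no SAEs, so the practical safety question for this pilot is about non-serious harms: exposure of personal details, upsetting content and discomfort. These are the harms for which no form has a dedicated item. The form that does exist covers only serious events and does not carry the full definition of serious.

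Two things are at stake. The first is coding: a serious event outside the four boxes would be reported without a recorded reason for its seriousness. The second is interpretation. If nobody asks about a harm, a count of zero does not show that it was rare. The pilot is meant to inform the UH3 trial, in which a closed WhatsApp group is a candidate intervention. A pilot that cannot say how often group members had a privacy or conduct problem leaves that part of the decision without data.

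**Working it through.** The plan states no figure on this point. The check is a comparison of texts, followed by one short calculation.

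**Step 1. SAE definition against SAE form, section A, item 5.**

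| Category in the definition | Box on the form |
|---|---|
| Death | Yes |
| Threat to life | Yes |
| Hospitalization, new or prolonged | Yes |
| Incapacity or disruption | Yes |
| Birth defects | No |
| Other important medical events | No |

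Six categories less four boxes leaves two that cannot be marked. The item allows several boxes to be ticked but has no write-in box. Birth defects are improbable in a six-month messaging trial, so the gap that matters in practice is the last row.

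**Step 2. Unanticipated-problem criteria against SAE form fields.** The form records the primary event, dates, seriousness, status, a narrative and the site physician's details. Structured fields for the three criteria (unexpected, related, greater risk): 0 of 3. The narrative asks for the event to be set in the context of the participant's study experience, but it does not ask for a judgement on cause or expectedness.

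**Step 3. Where a named non-serious harm could be recorded.** None of the 18 listed study tools is a form for non-serious events or unanticipated problems. What remains is incidental:

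- Protocol Deviation Form: an open category with a narrative. One participant passing on another's number is not clearly a protocol deviation.
- Withdrawal Form: an open reason, which reaches only those who withdraw.
- Moderator monitoring: no log is specified, and misuse outside the group is not visible to the moderator.
- Docu-drama focus group guide: asks whether the message might upset people. It covers the non-randomized test-run of 10.
- WhatsApp focus group guide: asks what hindered active participation, but not about harm.
- Month 6 CRF: proxies only. Item N.9 rates conflict with other donors, N.8 rates feeling alone as a donor, and P.1.c can record a failed venipuncture. There is no question on hospitalization, disclosure of personal details or upsetting contact.

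**Step 4. What asking would buy.** With n respondents and zero events, the one-sided 95% upper bound p solves (1 − p)^n = 0.05, so p = 1 − 0.05^(1/n). The values of n come from Pilot RCT sample size: 64 per arm targeted, 59 effective after the planned loss.

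- n = 64: 1 − 0.05^(1/64) = 0.0457, about 4.6%.
- n = 59: 1 − 0.05^(1/59) = 0.0495, about 5.0%.

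Without the question, n is not the number of participants but the unknown number who would have volunteered the information, and no bound follows.

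**The case against.** The strongest reply is that partial capture exists and that the risks are small. The narrative lets a site describe any event, including its link to the study. Deaths have their own CRF. Life-threatening events, hospitalizations and incapacity can all be coded, and a serious COVID-19 illness would reach the SAE form. The protocol calls the named risks minimal, and the gap does not touch the estimates of return donation or retention. All of this stands, and it limits the point to safety data.

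A reader might infer more than the documents support:

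- *That the DSMB would see an empty record.* This does not follow. Four SAE categories can be coded, the DSMB also reviews data quality and enrollment, and the BLOODSAFE DSMB charter, which may set the content of safety reports, is not part of the documents. The participant information sheets might also name a reporting route.
- *That no breach or distress could ever be recorded.* The routes in Step 3 could pick up some. They are incidental rather than systematic.
- *That the Unanticipated Problems section obliges the SAE form to carry relatedness and expectedness.* It defines the term and names no form. The fields would support the assessment; the text does not mandate them there.
- *That weekly messages in the WhatsApp arm would badly skew spontaneous reports between arms.* Those are group posts, both arms receive the standard calls, and harms from group membership cannot arise in controls. This should not be pressed.

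None of these limits closes the mismatch in item 5 or supplies a question about the named harms.

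**Conclusion.** The concern holds in a limited form. Two of the six SAE categories cannot be coded for seriousness. The SAE form has no structured relatedness or expectedness field. No CRF systematically asks about the non-serious harms the protocol names. The documents therefore provide no systematic by-arm tally of these harms for the DSMB's aggregate assessment, and zero reported events would be uninformative for UH3. If participants were asked, zero events would bound the rate below about 4.6% (64 respondents) or 5.0% (59 respondents) in an arm.

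This rests on two assumptions: that the charter and the participant-facing documents add no systematic collection of these harms, and, for the bounds, that respondents report events when asked. The change should be made before Month 6 calls begin. It does not affect the primary outcome.

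**What to change.** 1. Reconcile SAE form section A, item 5 with the Safety Assessment section by adding boxes for birth defects and for other important medical events.
2. Add two fields to the SAE form to support the unanticipated-problem assessment: relatedness to participation (not, possibly, probably, definitely) and expectedness (yes, no).
3. Add a short block to the Month 6 CRF, asked identically in both arms, covering the time since enrollment: any hospitalization; any disclosure or misuse of name, number or donor status; any upsetting message, image or contact linked to the study.
4. Have the existing WhatsApp moderator log removed posts and complaints.
5. Tabulate items 3 and 4 by arm in the DSMB closed report. List docu-drama test-run events separately, because that group is not randomized.

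The cost is a revision of two CRFs, a simple log, and about one minute more in a call already planned at about 30 minutes. The downside is that some minor events will now be counted. The design, the sample size and the primary analysis do not change.

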In sequence, this pilot study and larger RCT are grounded in the PRECEDE-PROCEED implementation science framework. This study has four components 1) a qualitative component (workshop) will be used to design a docu-drama (to be incorporated into the larger study), 2) Key informant interviews to guide intervention development 3) a simultaneous pilot RCT will evaluate the feasibility and the proportion of successful return blood donation for planning the larger trial design of the communication interventions using WhatsApp and control, and 4) a final mixed-methods (quantitative survey and focus groups) assessment of participant views of acceptability, effectiveness, feasibility and cultural appropriateness of all of the proposed communication interventions intended for the larger UH3 RCT to be administered after completion of the pilot trial prior to the UH3 phase.

The PRECEDE-PROCEED framework planning tool will be used to develop and evaluate the three strategies (Figure 3) and will incorporate the Theory of Planned Behaviour (Figure 4) and Technology Acceptance Model (Figure 5).

PRECEDE-PROCEED Framework

PRECEDE provides a planning approach to help create our interventions whereas PROCEED, aids the implementation and evaluation of the interventions to be designed in the PRECEDE part of the model.

[figure not shown]

Figure 2: PRECEDE-PROCEED Model that guides the study

Planning Model Component: Five Phases

We will use the following PRECEDE strategies during the UG3 phase:

First, we will conduct a systematic literature review of the effectiveness of social behavioural interventions including the use of drama for aiding blood donation in low-and middle-income countries. Second, we will conduct key informant interviews with four key stakeholders, with a minimum analysis sample of 24, comprising of: a) Blood Donors (n=6), b) Non-blood Donors (n=6), c) Blood Donation Staff (n=6) and d) community leaders (n=6) in the Greater Accra area of Ghana to seek their perspectives on how to encourage repeat blood donation. The sample size, as recommended for qualitative studies, will be increased if saturation is not reached (Saunders et al., 2018). Blood donors usually donate in groups in the community - such as social clubs, community youth clubs, religious groups etc. Blood donors will be selected

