from a list provided by the Blood Donor Recruitment Officers or volunteers (Blood Donor Recruitment Officers are on the staff of the NBSG who work with donors; volunteers are liaison persons between the community groups and the blood center. Both groups recruit blood donors and can advise on non-donors within their groups). Non-donors will be selected purposively from communities within which blood donation sessions are held, to ensure that the non-donors have been exposed to blood donation education just as the donor. The non-donor is a person who is qualified to donate but has never donated and does not intend to donate on the day of the interview.

Third, we will organize a drama design workshop with at least 20 key stakeholders including blood donors, drama actors and drama production experts.

All qualitative data collection will be conducted by trained researchers with social science and qualitative research background. A training manual will be developed for the training which will be conducted prior to data collection.

The activities will help the team to identify barriers, opportunities and recommendations that will inform the development and guidelines for implementation of the docu-drama and WhatsApp weekly messages to promote blood donation in Ghana. Specifically, the five PRECEDE phases will be addressed as follows:

Phase 1: Social Assessment

We will use the proposed systematic review, in-depth interviews and drama design workshop to explore and understand the need for creating socio-behavioural interventions to aid blood donation in Ghana.

Phase 2: Epidemiological assessment

We will use the findings of the systematic review and other data collected in Phase 1 to identify the evidence around repeat donations among first-time blood donors. This will include assessing current information on the proportion of first-time donors who become repeat donors. Information will be obtained from National Blood Service Ghana records and published literature in Ghana and elsewhere in sub-Saharan Africa.

Phase 3: Behavioural and Environmental Assessment

We will use both primary data (key informant interviews) and secondary data (for example, the findings from the systematic review) to identify donor factors and service factors, that affect the subsequent blood donation efforts of first-time blood donors.

Phase 4: Educational and Ecological Assessment.

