5. Mapping and interpretation: The research team will analyse key characteristics as laid out in the charts and generate a schematic diagram of the key themes. This will include creating typologies, finding associations, providing explanations, and developing strategies.

Data will be coded and analyzed for themes using the Qualitative Software and Research (QSR) Nvivo Release 1.0 (Released March 18, 2020).

Information from the different qualitative methods will be linked to the focus of the study as follows:

1. **Key informant interviews:** These will be used to get information that will help the research team to identify challenges and motivations for first-time blood donors to repeat donation among respondents. The information will help in creating the study interventions.
2. **Design workshop:** Information from the design workshop will be used to create a design document to guide the scriptwriter to produce a script that truly captures the focus of the drama intervention.
3. **Focus group discussions:** Information from the focus groups will be used to identify what worked and what did not work well for the interventions, and to assess the acceptability, *feasibility and cultural appropriateness of the interventions.*

Quantitative Data Analysis

Statistical analysis will be completed using SAS or R.

Analysis pilot trial:

The analysis for the pilot study is to inform the planned larger UH3 randomized controlled trial and will follow the same anticipated primary analysis (see below) with acknowledgment of low power to evaluate effectiveness.

The feasibility of the larger study will be assessed with descriptive statistics for enrollment rates, retention, and adherence. Key blood donation measures needed to inform the design of the larger UH3 randomized controlled study will be analyzed and include the proportion of participants who return to the blood centre to donate blood.

Primary analysis (anticipated) for the larger UH3 randomized controlled trial:

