2. Again, there are no right or wrong answers and it's okay to be critical. I want to hear your views and opinions about whether you like or dislike something you see or hear.
3. You may excuse yourself from the conversation at any time for any reason.
4. Although this session will be audio taped, it will remain confidential and will ONLY be used to capture everything that is being said today, for the purpose of listening to it again to get the message well. Please feel free to say exactly what is on your mind as nothing will be attributed to any particular person in our report.

A. WhatsApp Intervention

Demographics

- What is your name?
- How old are you?

Knowledge

- What is the potential of using WhatsApp for promoting blood donation?
- What do you consider as advantages of using WhatsApp to encourage blood donation?
- What do you consider as disadvantages of using WhatsApp to encourage blood donation?

Beliefs

- Do you believe that WhatsApp can be used to promote blood donation? If yes, why? If no, why not?

Attitudes

- How will you feel if your friends, relatives or others you respect found out that you are in a WhatsApp group that promotes blood donation?
If positive, explain why
If negative, explain why

Challenges, opportunities and recommendations

We will be designing WhatsApp intervention for promoting blood donation. Group participants will be expected to share information on their blood donation experiences to encourage others to donate blood. A moderator will also post relevant items periodically.

- Have you used WhatsApp for health promotion activities? If so, was it positive or negative and explain why?
- What do you foresee as potential challenges in the design of WhatsApp intervention for promoting blood donation?
- How can we address these challenges?
- What suggestions do you have for making such an intervention successful?
- How many times should a moderator post an item in a week and why?
- What further comments do you have on the intervention?

B. Docu-drama intervention

Demographics

- What is your name?
- How old are you?

Knowledge

- What is the potential of using video documentary with drama (docu-drama) for promoting blood donation?
- What do you consider as advantages of using docu-drama to encourage blood donation?
- What do you consider as disadvantages of using docu-drama to encourage blood donation?

Beliefs

- Do you believe that docu-drama can be used to promote blood donation? If yes, why? If no, why not?

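### The key informant interview guide does not directly ask what makes first-time donors return or stay away, although the plan names these interviews as a primary source for exactly that

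*Combined protocol and SAP*

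**What the plan says.** The protocol gives the key informant interviews several tasks.

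- **Study Design, Planning Model Component:** interviews with six people from each of four groups (blood donors, non-donors, donation staff, community leaders) are to "seek their perspectives on how to encourage repeat blood donation".
- **Phase 3, Behavioural and Environmental Assessment:** the interviews are the named primary data, alongside secondary data, "to identify donor factors and service factors, that affect the subsequent blood donation efforts of first-time blood donors".
- **Phase 4, Educational and Ecological Assessment:** the interviews, with previous Ghanaian data, are to identify predisposing, enabling and reinforcing factors, which are then ranked.
- **Qualitative Data Analysis, step 2:** "The themes will include barriers to becoming a repeat donor and motivations for being a repeat donor". It adds: "These themes will be used to guide intervention development, and to assess secondary outcomes".
- **Qualitative Data Analysis, item 1:** the interviews will "help the research team to identify challenges and motivations for first-time blood donors to repeat donation among respondents", and "The information will help in creating the study interventions".

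Two other places are narrower. Primary Objectives, item 1, assigns docu-drama development to the workshop and has the interviews guide the WhatsApp intervention. Under Sample Size Assumptions, the 24 interviews are to show how the WhatsApp platform will be used.

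The only key informant guide in the documents is Study Tool 1. It has a WhatsApp part and a docu-drama part. A typical item reads "What do you foresee as potential challenges in the design of WhatsApp intervention for promoting blood donation".

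**The concern.** An interview can be relied on only for what it asks. The analysis fixes barriers to and motivations for repeat donation as themes in advance, but the guide asks what respondents think of WhatsApp and docu-drama as means of communication. The block labels (Knowledge, Beliefs, Attitudes, Challenges) look like donor constructs, yet the items beneath them concern the channel.

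The content of the interventions is at stake. The Study Interventions section expects the docu-drama to deal with donors' worries about giving blood a second time. The Planning Model text expects the formative work to inform the weekly WhatsApp messages. If the guide is used as written, primary data on those worries will depend on what respondents happen to volunteer. That is a weak basis for ranking factors, as Phase 4 intends.

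**Working it through.** No power or precision formula applies. The check is a count and a comparison of texts.

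**1. The plan's own figure.** Four groups of six give 4 × 6 = 24 interviews. This matches the minimum in the Planning Model text and the number under Sample Size Assumptions.

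**2. Items in Study Tool 1, leaving out name and age.**

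| Block | WhatsApp | Docu-drama | Subject |
|---|---|---|---|
| Knowledge | 3 | 3 | potential, advantages and disadvantages of the channel |
| Beliefs | 1 | 1 | whether the channel can promote donation |
| Attitudes | 1 | 1 | feelings if others learned of group membership |
| Challenges, opportunities, recommendations | 6 | 7 | past use for health promotion, design challenges and remedies, suggestions, posting frequency or discussion length and content, further comments |
| Total | 11 | 12 | |

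11 + 12 = 23. Items that directly ask about reasons for returning or not returning, or about service factors: 0 + 0 = 0. No question refers to first-time donors or to donating a second time, and no probes on these subjects are listed.

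**3. Assigned task against guide.**

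- *Challenges to repeat donation (Qualitative Data Analysis, item 1).* The guide's challenges items concern the design of the WhatsApp or docu-drama intervention.
- *Motivations for repeat donation (step 2).* No direct item. The nearest are the advantages of the channel and suggestions for making it succeed.
- *Donor and service factors (Phase 3).* No direct item on fears, experience at the session, access, or recall of donors.
- *Views on encouraging repeat donation (Planning Model).* Partly met: the advantages and suggestions items touch encouragement, but through the channel and not for repeat donation in particular.
- *How the WhatsApp platform will be used (Sample Size Assumptions).* Met.

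**4. Who is asked.** The same items go to all four groups. Six of the 24 are blood donors, and the selection text does not require those six to be first-time donors. The other 18 (24 − 6) could speak about return only from observation.

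**5. Whether other new data fill the gap in time.**

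- *Workshop guide (Study Tool 2):* name, tone, objectives, key messages and episode order. No item on barriers or motivations.
- *Docu-drama focus group guide (Study Tool 3):* asks what would encourage or discourage acting on the message, but only after the drama has been made and shown.
- *Month 6 form (Study Tool 10, section P):* asks why a participant did not donate, with a coded list of reasons, after the six-month WhatsApp intervention has run.

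**The case against.** The strongest reply has four parts.

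**Open items may supply the content.** Respondents are asked for suggestions, for what should be discussed after the drama, for how they would feel if relatives knew of their membership, and for further comments. The framework analysis keeps emergent themes. This stands. A reader might infer that the interviews cannot yield barriers or motivations at all, and the documents do not support that. They support only that the guide does not directly ask.

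**The interviews are one source among several.** The plan also names a new systematic review, National Blood Service records, previous data on first-time donors in Ghana, and the workshop. The Background already lists local motivators and deterrents. This stands too, so it would be wrong to infer that the interventions would rest on old literature alone. It does not answer the point that Phases 3 and 4 promise primary data from these interviews.

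**The interviews have a narrower job.** Primary Objectives and Sample Size Assumptions tie them to WhatsApp, and the guide serves that purpose. This is correct, and it rules out saying that both interventions depend on the interviews. But the title of Study Tool 1 covers both interventions and item 1 of the qualitative analysis speaks of the study interventions generally. The narrower purpose therefore shows that the protocol disagrees with itself.

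**The themes also cover focus groups.** The framework analysis applies to interviews and focus groups together, and the focus group guides ask about influence on the intention to return. This stands for the later assessment. It does not help before the piloted WhatsApp content is written.

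**Conclusion.** The mismatch is real. None of the 23 substantive questions directly seeks what Phase 3, Phase 4 and the Qualitative Data Analysis section say these interviews will provide, and all 24 interviews are affected. The gap is in primary data on barriers, motivations and service factors before intervention development. The protocol's statements of what the interviews are for also differ.

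This rests on the guide being used as written and on its being the only key informant guide; interviewers who probe freely could narrow the gap. The count describes questions and does not measure information lost.

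The point bears on the formative objective. Randomisation, the primary outcome and its analysis are untouched, and nothing here suggests that the comparison of WhatsApp with control would be biased. It should be corrected because the remedy is small and intervention development is a primary objective.

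**What to change.** Add four or five open questions with probes to Study Tool 1, ahead of the channel questions and worded for each group:

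- *Donors:* what would bring them back, what would keep them away, and what in their experience of the service helped or hindered. Record whether the respondent is a first-time donor.
- *Non-donors:* what has held them back, and what they hear from donors about giving a second time.
- *Staff:* which procedures, resources or policies help or limit the return of first-time donors.
- *Community leaders:* what in the community, including beliefs, family views, cost, distance and time, encourages or discourages return.

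The cost is resubmission of the guide to the ethics committees and longer interviews. The documents give no figure for the added time. At an assumed 10 minutes each, the total is 24 × 10 = 240 minutes, or 4 hours. At half or double that, it is 2 or 8 hours.

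At minimum, reconcile the Planning Model text, Phases 3 and 4 and the Qualitative Data Analysis section with Primary Objectives and Sample Size Assumptions, so that one purpose is stated for the interviews. Then name where the barrier and motivation data will come from, for example the review, service records and previous Ghanaian data. This costs only a text amendment, but it gives up the primary data.
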